##### Recruiting Service Members

Will you be recruiting service members in a group setting?

Yes

No

##### Participation Compensation:

Participants will not be compensated.

##### Assent Process: N/A

##### Benefits:

The primary benefit of this research on subjects is a potential improvement in their osteoarthritis-related knee pain; however, this is not a guarantee.

##### Risks:

Breach of confidentiality of the data is a potential risk. Every effort will be made by the study team to protect the study data. This study otherwise holds minimal risk to the participant. Given use of third party mobile applications, there are additional risks based on participants' study cohort:

Participants in Group 1 will be asked to agree to the Terms and Conditions and Privacy Policy of the Headspace application during registration. As outlined in these documents, Headspace will maintain a record of an individual's name and email address. They will also track time spent on the application, the specific mindfulness sessions or packs employed, and the

operating system upon which the app was accessed (iOS, Android, etc.). While this information is stored on an encrypted server, there is a risk of a security breach that would result in this data being compromised. Cookies may be used to store login information and remember user preferences in the application. While not a component of registration for this study, it is possible to link one's account with social media accounts such as Facebook. Linking one's social media account is not recommended and may result in compromise of more data, including Facebook profile information.

Participants in Group 2 will be asked to download and My Water Balance on their personal smart phone. This application will store screenname, email address, password of choice, gender, and weight. In addition, they may store participants' recorded intake of water. During initial application setup, the app will be denied access to users' geographic location; however, there is a risk that individual users may reverse this option and the application may store this information. This information may be stored on a third party server and is subject to security breach and loss of confidentiality.

As a free application, users will be exposed to ads and will be offered the chance to upgrade to an ad-free, paid version. All will be advised to not make any in-application purchases as a part of this study. It is possible to link use of this application to one's social media account on Facebook, Twitter, and Instagram. Doing so will allow the application to store their social media information, including username and profile contents. Users will be advised that linking one's social media account is not recommended and may result in compromise of more data.

**Costs:** N/A

#### Safeguards for Protecting Information:

##### Data and Specimen Storage Plan

##### How will coded or identifiable data/specimens be stored?

	Paper data, including completed consent forms	The research consents and HIPAA Authorization Documents will be stored in a locked cabinet in a locked room with restricted access.
	Electronic data	Medical records will be annotated to reflect the subject's participation in a research study. All coded, de-identified research data will be electronically stored separately from the Master Key of identifiable patient demographics and PHI/PII at each site.
	Long-term storage (following completion of the study and inactivation of IRB approval)	The research data will be coded and any links to identifiable data will be destroyed (an approved shredding bin) as soon as possible as or no later than at the closure of the study. The anonymized research data will not be utilized for further research activity beyond the protocol stipulations without additional IRB approval. All de-identified research data will be maintained for 3 years following study closure.

#### Safeguards for Protecting Subjects Relative to Reasonably Expected Risks:

Safeguards are in place for protecting subjects and their health data. The research consents and HIPAA Authorization Documents will be stored in a locked cabinet in a locked room. Risks related to participating will be minimized, as the subjects do not have to participate or answer any question that they do not want to complete. If at any time the patient reports a side effect, they will be referred to one of the Investigators for care.

**Categories of subjects** | N/A

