#### **Visit 1 (Baseline, in-person visit):**

- All participants will receive patient education regarding osteoarthritis, its natural history, and common treatments.
- All will receive education about the Rx3 Home Exercise Program, which serves as a physical intervention for pain management.
- All participants will be asked to perform the Rx3 Home Exercise Program 3 times weekly.

- All participants will be assigned a study ID# and will be given the on-line baseline Knee injury and Osteoarthritis Outcome Score (KOOS), Short Form-12 (SF-12), and Five Facet Mindfulness Questionnaire-15 (FFMQ-15) surveys using Google Forms or Survey Monkey.
- All participants will receive instructions per the randomization instructions above.
- All participants will be given a Medication Diary to complete on a weekly basis.

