**Weeks 2-11:**

Participants will receive **weekly** reminders (via email) asking that they use the app throughout the week. They will also be asked to fill out a short Weekly Survey inquiring:

- Frequency and minutes used for the intervention (My Water Balance and Mindfulness app 10 minutes per day/5 days per week)
- Frequency and minutes spent performing the Rx3 Home Exercise Program in the past week (3 times weekly)
- Use of NSAIDs or other over-the-counter pharmacologic methods of pain control in the past week.

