**Visit 2 (Week 12, electronic contact):**

Participants will complete the following surveys and asked the following questions via Google Forms or Survey Monkey. These anonymous forms will be completed via Google Forms or Survey Monkey and the results transcribed to a master excel file for centralized data tracking. Each subject will use their pre-assigned study code to record on each completed questionnaire:

- KOOS
- FFMQ15
- SF-12
- 12-Week survey to evaluate for treatment response to the Rx3 Home Exercise Program and mindfulness app intervention.
- Group 1 (intervention group): Following completion of the 12-week intervention period, participants will no longer have free access to the Headspace application.
- Group 2 (control group) will be asked to cease the use of the My Water Balance application.

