**Visit 3 (Week 26, electronic contact):**

Participants will complete the following surveys and asked the following questions via Google Forms or Survey Monkey:

- KOOS
- FFMQ15
- SF-12
- Groups will be queried on their continued use of the Rx3 Home Exercise Program, and over-the-counter analgesic use.
- Group 1 (intervention group) will be queried on continued employment of mindfulness techniques.
- Group 2 (control group) will be queried on continued use of diet and exercise techniques.

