#### Clinical Care:

If at any time a subject experiences any injury or adverse effects, appropriate clinical care will be given or subject will be referred to appropriate provider.

**Injury Compensation:** N/A

**Data Safety Monitoring** |  N/A – none of the situations listed above apply

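### As the protocol body describes them, none of the 14 post-baseline contacts asks about injury or side effects and no harms summary is planned, so attributed harms depend on volunteering unless the unsupplied forms already ask

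*Combined protocol and SAP*

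**What the plan says.** Section 4 covers harms in two places. Under the safeguards heading: "If at any time the patient reports a side effect, they will be referred to one of the Investigators for care". Under Clinical Care: "If at any time a subject experiences any injury or adverse effects, appropriate clinical care will be given". Both say what happens once a problem is known. Neither says how it would be found, recorded or summarised. Data safety monitoring is marked not applicable.

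The exercise programme is assigned to both arms: "All participants will be asked to perform the Rx3 Home Exercise Program 3 times weekly". The procedures table in section 3f counts it as 36 research-driven sessions per participant and none as routine care.

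Section 3 describes the contacts after baseline, all of them electronic:

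- **Weeks 2-11.** "They will also be asked to fill out a short Weekly Survey inquiring" about three topics: app use, Rx3 use, and "Use of NSAIDs or other over-the-counter pharmacologic methods of pain control in the past week".
- **Week 12.** KOOS, FFMQ-15 and SF-12, plus a "12-Week survey to evaluate for treatment response to the Rx3 Home Exercise Program and mindfulness app intervention".
- **Weeks 26, 52 and 104.** The same three questionnaires, and "Groups will be queried on their continued use of the Rx3 Home Exercise Program, and over-the-counter analgesic use". Each arm also gets a question on continued techniques.

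A weekly Medication Diary runs alongside: "All participants will be given a Medication Diary to complete on a weekly basis". The outcomes in section 3a are KOOS, FFMQ and SF-12. Section 6 plans efficacy, moderator and subgroup analyses, and a post-hoc look at medication use as a confounder.

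**The concern.** The trial asks adults up to age 74 with symptomatic knee osteoarthritis to exercise three times a week for research purposes, and after baseline it contacts them only electronically. No later visit gives staff a routine chance to notice a problem. If no form asks, the report can show changes in KOOS and SF-12 and in analgesic use, but not a solicited count of injuries, falls or other problems that participants attribute to the exercise or the app. Indirect measures cannot separate an exercise injury from progression of the arthritis.

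The follow-up rule adds to this. Participants who do not return the end-of-intervention surveys after three reminders are removed, and anyone who misses one set is not asked for the next. Someone who stops because of a problem may therefore never be asked why.

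**Working it through.** **1. Count the contacts.** The procedures table gives five administrations each of KOOS, FFMQ-15 and SF-12. The schedule reproduces this: baseline plus weeks 12, 26, 52 and 104 = 5, so 4 fall after baseline. Weekly surveys in weeks 2 to 11 inclusive number 10. Total: 10 + 4 = 14.

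**2. Check each contact for a harms question.**

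| Contact | Number | Content described | Asks about injury or side effects? |
|---|---|---|---|
| Weekly Survey | 10 | App use, Rx3 use, analgesics | Not described |
| Week 12 | 1 | Three questionnaires, treatment response | Not described |
| Weeks 26, 52, 104 | 3 | Three questionnaires, continued use, analgesics | Not described |

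Result: 0 of 14. Harms outcomes in section 3a: none. Harms summaries in section 6: none.

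**3. What one item would allow.** With zero events among n people who answer, the one-sided 95% upper bound on the event rate is 1 - 0.05^(1/n). A weekly item also reaches people who later drop out, so n is the number who answer at least once. Take as the range all enrolled (180 per arm, 360 in total) down to 25% loss (180 × 0.75 = 135; 360 × 0.75 = 270), both from section 6. The completion figure in the Number of Subjects table (3 × 96 = 288, or 144 per arm) lies inside it.

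| Group | n | Bound |
|---|---|---|
| Per arm, all answer | 180 | 1.65% |
| Per arm, 25% loss | 135 | 2.19% |
| Pooled, all answer | 360 | 0.83% |
| Pooled, 25% loss | 270 | 1.10% |

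Both arms do Rx3, so a comparison by arm says little about exercise harm. The pooled rows apply to Rx3-related events and the per-arm rows to app-related events.

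**4. Workload.** Forms through week 12: (10 + 1) × 360 = 3,960 at most. The documents give no yes rate, so assume 1-5%: 0.01 × 3,960 = 39.6 and 0.05 × 3,960 = 198. Over three sites that is about 13 to 66 each.

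**The case against.** **The forms may already ask.** The Weekly Survey, Week 12 survey, diary, email script and consent document are listed in section 12 but were not supplied. The body only summarises the surveys, and a question on response to Rx3 could include a bad response. This stands: a reader might infer that harms are certainly not collected, and the documents do not show that. The caveat is weaker for weeks 26-104, where no separate attachment is listed for the extra questions. It does not touch the absence of a harms summary in section 6.

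**The likeliest exercise harm is already solicited.** Worse knee pain or function would show in KOOS, whose pain subscale is the primary outcome. This also stands. What remains uncollected is narrower: attributed injuries and problems outside the knee.

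**Missed events might be recoverable.** A reader might infer that unasked events are lost for good. Participants are beneficiaries recruited through the sites' own clinics, their records are reviewed at screening and annotated with participation, and the key survives until the final report is approved. Injuries that led to care might be found by chart review. No such review is planned and its authorisation is not shown, but permanent loss is not established.

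**The study is described as minimal risk**, and it excludes people with a condition contraindicating moderate aerobic exercise. This supports a low priority. A reader who inferred that participants are being harmed, or that the efficacy result is biased, would find no support in the documents.

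**Conclusion.** The point holds as a minor improvement to safety ascertainment. In the protocol body, 0 of 14 post-baseline contacts are described as asking about injury or side effects, and no harms summary is planned. If the unsupplied forms do not ask, attributed injuries and non-knee problems from Rx3 or the app depend on participants volunteering them. If they do ask, only the missing summary remains.

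The primary result is unaffected. The bounds of about 1.7-2.2% per arm and 0.8-1.1% pooled show what asking could establish if no event occurred. They apply only to people who answer, and they are not estimates of harm.

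**What to change.** First check the attached forms. Unless they already ask, add one yes/no item, worded identically in both arms, to the Weekly Survey (weeks 2-11) and the Week 12 survey:

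*Since your last survey, have you had an injury, fall or other problem that you think is related to the exercise program or the app?*

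Put no free-text health details on the third-party form. The existing Research Coordinator at each site, who holds the key, follows up each yes, records in the study's own coded file whether it was linked to Rx3, the app or neither, and refers under the safeguard already in section 4. In section 6, plan one table: Rx3-related events pooled over arms and app-related events by arm, with the number who answered at least once as denominator.

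**Cost.** A short IRB amendment, one table, and about 40-198 follow-ups at the assumed 1-5% yes rate. Confidentiality is the main named risk, and there is a real cost here. Each yes must be re-linked by the key-holder, and a coded yes sits on a third-party form under a study code built from site, initials and four phone digits.

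**Weeks 26, 52 and 104 are optional.** App provision has ended, recall windows are 14, 26 and 52 weeks, and earlier non-responders are no longer queried. Keep the item limited to problems the participant attributes to the exercise or the app. If it also counted anything that needed care, and 20-40% said yes on the 3 × 360 = 1,080 later forms (an assumption), those forms alone would add 216-432 follow-ups for little gain.

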#### Clinical Care:

If at any time a subject experiences any injury or adverse effects, appropriate clinical care will be given or subject will be referred to appropriate provider.

**Injury Compensation:** N/A

**Data Safety Monitoring** |  N/A – none of the situations listed above apply

## 5. ALTERNATIVES

#### Alternatives:

The alternative is not to participate in this research study and to receive standard of care.

## 6. DATA ANALYSIS

### Data Analysis:

### Outcome Measures:

To compare the effect of the mindfulness app intervention against the control: using an intention-to-treat paradigm, the two groups will be compared via one-way analysis of variance (ANOVA).

To compare the effect of a mindfulness app intervention among high and low strata of baseline pre-intervention SF-12 and FFMQ-15 scores: statistical calculation is based on the interaction effect in a 2-way analysis of variance (ANOVA) model with 5% two-sided significance level.

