**a. Interventions and Observations:**

Participants will be re-surveyed at 12, 26, 52, and 104 weeks to evaluate long-term outcomes. The primary outcome measure will be post-intervention change in Knee injury and Osteoarthritis Outcome (KOOS) pain subscale. Secondary outcomes will include the other KOOS subscale scores, FFMQ outcomes, and SF-12 self-reported mental and physical health self-assessments at these same time intervals.

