### Sample Size Estimation/Power Analysis:

Based on the KOOS Minimal Detectable Changes in patients with knee OA of 10 with a Standard Deviation of 15, a sample size of 74 per group will have 80% power to detect such a difference based on Student's t test for independent samples with 5% two-sided significance level. Allowing for 25% dropout, the required sample size is 99 per group to accomplish the first aim.

However, to determine if high or low strata of baseline mindfulness affects pain outcomes, a sample size of 144 per group (72 in each SF12 stratum) will have 80% power to detect a difference of 10 points with a standard deviation of 15 points (i.e., no mindfulness effect in the high SF12 stratum vs. a 10-point mindfulness effect in the low SF12 stratum). Allowing for the aforementioned 25% dropout rate, we anticipate 180 participants per group or 360 total participants.

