### Statistical Analysis:

Using an intention-to-treat paradigm, the first primary aims will be statistically compared via one-way analysis of variance (ANOVA). The second primary aim will be statistically compared via two-way analysis of variance (ANOVA).

Missing primary outcome data will be acknowledged in the overall report of analysis. The primary outcome data is based on KOOS scoring system. Per the validated instructions of KOOS analysis, "as long as at least 50% of the subscale items are answered for each subscale, a mean score can be calculated. If more than 50% of the subscale items are omitted, the response is considered invalid and no subscale score should be calculated." In the event that the KOOS data is omitted, the participant will be regarded as a "drop out" and they will be included as such in the intent-to-treat analysis.

Subgroup analyses will be completed via 2-way ANOVA, stratified by FFMQ-15 and SF-12 scores. Subgroup analysis based on age, gender, comorbid behavioral health conditions, and duration of Knee OA symptoms may be considered.

Over-the-counter pharmacologic treatment of musculoskeletal pain is a common practice; given the near ubiquitous usage of these medications, this protocol does not preclude use of NSAIDs or acetaminophen. However, medication use will be monitored via weekly surveys and analyzed post-hoc as a potential confounder of the collected data.

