### Number of Subjects:

	# Planned to Enroll	# Enrolled	# Planned to Complete Study	TOTAL
Number of Subjects at Scott AFB	120	0	96	360
Number of Subjects at Travis AFB	120	0	96	
Number of Subjects at Nellis AFB	120	0	96	

*\*If any location recruits more subjects, they will be allowed to continue recruiting not to exceed the total number of subjects for all locations.*

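### The planned ANOVAs of change in KOOS pain leave out baseline KOOS pain as a covariate; adding it narrows the Aim 1 interval and raises Aim 2 interaction power at almost no cost.

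*Combined protocol and SAP*

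**What the plan says.** Section 3a (Interventions and Observations) defines the endpoint: "The primary outcome measure will be post-intervention change in Knee injury and Osteoarthritis Outcome (KOOS) pain subscale". Section 6 names the tests twice. Under Outcome Measures, "using an intention-to-treat paradigm, the two groups will be compared via one-way analysis of variance (ANOVA". Under Statistical Analysis, "the first primary aims will be statistically compared via one-way analysis of variance (ANOVA" and "The second primary aim will be statistically compared via two-way analysis of variance (ANOVA". Outcome Measures makes the Aim 2 test the interaction of arm with high or low baseline SF-12 and FFMQ-15 stratum.

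In Section 3, Visit 1, all participants "will be given the on-line baseline Knee injury and Osteoarthritis Outcome Score (KOOS"), so baseline KOOS pain will be available. No section enters it, or any other continuous baseline variable, as a covariate. The words repeated measures appear only in the randomization sentence and are not carried into the analysis. The post-hoc look at medication use in Section 6 is not baseline adjustment.

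**The concern.** With two arms, a one-way ANOVA of change is a two-sample t test on change scores. Subtracting the baseline uses it with a slope fixed at 1. When the true slope of follow-up on baseline is below 1, as it is with equal variances and a correlation rho below 1, subtraction over-corrects: a chance baseline difference d between arms leaves -(1-rho) x d in the estimate. That is 30% of d at rho 0.7 and 70% at rho 0.3, with the sign reversed. ANCOVA estimates the slope and removes this part.

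Randomization makes these differences average to zero, so the planned estimate is unbiased, but they add variance. This matters most for the Aim 2 interaction, which sets the 360-participant target and has little power to spare.

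**Working it through.** **Inputs from Section 6.** Sample Size Estimation gives two-sided 5% significance, 74 per group for Aim 1, 144 per group (72 per arm-by-stratum cell) for Aim 2, 25% dropout and 180 enrolled per group. Aim 2 is powered "to detect a difference of 10 points with a standard deviation of 15 points"; Aim 1 uses the same difference and SD. The Number of Subjects table, in its column "Planned to Complete Study", lists 96 at each of three sites: 3 x 96 = 288, or 144 per group.

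**Assumptions not in the documents.** Equal KOOS pain variance at baseline and follow-up; rho of 0.3 to 0.7, with 0.9 as a stress case; 1:1 allocation and equal strata.

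**1. Reproduce the plan's Aim 2 figure.** The interaction contrast has SE = SD x sqrt(4/cell size). The normal approximation gives 4 x (15 x (1.960 + 0.842)/10)^2 = 70.6 per cell. The noncentral t gives 72 per cell, or 144 per group, with 80.5% power. The stated figure reproduces.

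**2. Power at the planned enrolment.** 180 x 0.75 = 135 completers per group, or 67.5 per cell: 77.9%. With the 144 completers per group in the Number of Subjects table: 80.5%.

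**3. Aim 1 power, unadjusted.** SE = 15 x sqrt(2/n). At 74 per group this is 2.47 and power is 98.1%. At 135 it is 1.83 and power is 99.98%.

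**4. Variance gain.** With score variance s^2, Var(change) = 2 x s^2 x (1-rho) and the ANCOVA residual variance is s^2 x (1-rho^2). The ratio is (1+rho)/2, and the interval shortens by 1 - sqrt((1+rho)/2).

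**5. If SD 15 is the SD of change.** The ANCOVA residual SD is 15 x sqrt((1+rho)/2). Half-widths are for 95% intervals, in KOOS points.

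| | Unadjusted | rho 0.3 | rho 0.5 | rho 0.7 | rho 0.9 |
|---|---|---|---|---|---|
| Variance ratio | 1 | 0.65 | 0.75 | 0.85 | 0.95 |
| Interval shortened by | - | 19.4% | 13.4% | 7.8% | 2.5% |
| Residual SD | 15.0 | 12.1 | 13.0 | 13.8 | 14.6 |
| Aim 1 half-width, 135 per group | 3.6 | 2.9 | 3.1 | 3.3 | 3.5 |
| Aim 2 half-width, 135 per group | 7.2 | 5.8 | 6.2 | 6.6 | 7.0 |
| Aim 2 power, 135 per group | 77.9% | 92.3% | 88.3% | 84.1% | 79.9% |
| Aim 2 power, 144 per group | 80.5% | 93.8% | 90.2% | 86.4% | 82.4% |

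At 144 per group and rho 0.3 to 0.7, the Aim 1 half-width falls from 3.5 to 2.8-3.2 points and the Aim 2 half-width from 7.0 to 5.6-6.4. Completers per group needed for 80% interaction power fall from 144 to 94, 108 and 122 at rho 0.3, 0.5 and 0.7.

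**6. If SD 15 is the SD of a single score.** The change SD is 15 x sqrt(2 x (1-rho)) = 17.7, 15.0, 11.6, and the ANCOVA SD is 15 x sqrt(1-rho^2) = 14.3, 13.0, 10.7, at rho 0.3, 0.5, 0.7. Aim 2 power at 135 per group goes from 63.5%, 77.9%, 94.1% to 81.6%, 88.3%, 96.9%.

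**7. If the ANOVA were run on follow-up scores instead.** The interval would shorten by 1 - sqrt(1-rho^2) = 4.6%, 13.4%, 28.6%. ANCOVA is the more precise on either reading of the outcome.

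**8. Size of the residual imbalance.** With score SD 15, rho 0.5 and 135 per group, a one-SE baseline difference is 15 x sqrt(2/135) = 1.83 points. The change-score estimate keeps 0.5 x 1.83 = 0.91 of it.

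**9. Simulation check.** With 2,000 runs per setting, 68 per cell, rho 0.5 and the stratum correlated 0 to 0.6 with baseline pain, interaction power was about 79-81% unadjusted and 88-90% adjusted. The gain persists when the stratum is related to baseline pain.

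**The case against.** The strongest reply is that nothing in the plan is wrong here. An ANOVA of change scores in a randomized two-arm trial is valid and common, and it already uses the baseline by subtraction. That stands: the proposal is to estimate the slope rather than fix it at 1.

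Aim 1 does not need the power at a uniform 10-point effect, and its half-width improves by only 0.3 to 0.7 points at 135 per group. That also stands, with one qualification. In the plan's own Aim 2 scenario (0 points in one stratum, 10 in the other), the average effect is (0 + 10)/2 = 5 points. Aim 1 power at 135 per group is then 78% unadjusted and 84-92% adjusted.

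The fall from 80% to 78% for Aim 2 is not caused by the missing covariate. It arises because 180 is 144 x 1.25, while Aim 1 divided by the retained fraction (74/0.75 = 99). The same method gives 144/0.75 = 192, which restores 80% without adjustment. This is correct, and the inflation needs its own correction. It does not remove the gain at a given number of completers, as the 144 row shows.

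Finally, rho is undocumented, and the gain can be small: 78% to 80% at rho 0.9 on the change-SD reading, or 99.1% to 99.5% at rho 0.8 on the score-SD reading. So the documents fix the direction of the gain but not its size. Under the equal-variance assumption the gain does not reverse for any rho below 1.

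**Conclusion.** The concern holds as a point of efficiency, not validity. Both planned models omit a baseline measure that the trial already collects. For rho 0.3 to 0.7, ANCOVA shortens intervals by 19% to 8% relative to change scores. The main benefit is to Aim 2: about 6 to 14 percentage points of interaction power at 135 completers per group if SD 15 is the SD of change, and about 3 to 18 points if it is the SD of a single score. For Aim 1 the benefit is mainly a tighter estimate. These sizes rest on equal variances and an assumed rho. The change should be made, but the planned analysis would not mislead without it.

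**What to change.** In Section 6, under both Outcome Measures and Statistical Analysis:

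- **Aim 1:** replace the one-way ANOVA with ANCOVA of week-12 KOOS pain on arm, with baseline KOOS pain as a continuous covariate. Using change as the outcome gives the same arm estimate. Report the adjusted difference with its 95% confidence interval.
- **Aim 2:** fit arm, stratum, arm-by-stratum interaction and baseline KOOS pain.

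Two clarifications belong in the same edit but are separate gaps. State that week 12 is the primary time point, with weeks 26, 52 and 104 secondary. Section 3, Visit 2 implies this ("Following completion of the 12-week intervention period"), but Section 3a does not say it. State also whether SD 15 refers to a score or to a change.

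The cost is Section 6 wording and one degree of freedom per model; no new data are needed. The covariate should be fixed before outcome data are examined, because adjustment chosen afterwards invites doubt.
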